8.6.2.2. Measurements of Treatment Compliance

Treatment consists of parenteral opioid therapy administered by qualified medical personnel. There is no opportunity for self-administration outside of the confines of PCA, and the study drug is not dispensed to an enrolled patient outside of the confines of the investigative site. No summaries of compliance will be performed.

8.6.3. Adverse Events

The MedDRA version 19.0 will be used to classify all verbatim AE terms with respect to SOC and PT. Summaries will include only TEAEs and will be summarized for the Safety Analysis Set for each cumulative dose group and for all groups combined.

An overall summary of TEAEs will be performed with the following categories: any TEAE, serious TEAEs, TEAEs with the outcome of fatal, and TEAEs leading to early discontinuation. Severity rating and relationship to study medication categories will also be summarized. The summary will include unique patient counts and percentages based on the number of patients in the cumulative dose group, and the total event count. Overall summary of TEAEs will be repeated by sex, age grouping 1, age grouping 2, race, median baseline NPRS score, BMI, CYP2D6 metabolizer status and initial setting subgroups.

The number and percentage of patients with TEAEs for each cumulative dose group and overall will also be displayed by SOC and PT and will be repeated by BMI and CYP2D6 metabolizer status subgroups. These 3 summary tables will also be repeated for serious TEAEs and TEAEs leading to early discontinuation.

TEAEs will also be summarized by PT only. This summary table will be repeated by BMI and CYP2D6 metabolizer status subgroups.

TEAEs, serious TEAEs and TEAEs resulting in early discontinuation will be summarized by cumulative dose and cumulative time based on the time point intervals defined in section 6.2.4. TEAEs by cumulative dose and cumulative time based on the time point intervals will also be summarized by PTs.

A summary of most common TEAEs will be presented, where PTs occurring in at least 5% of the all treated patients group will be included. Summaries will be sorted by PT in descending frequency in the all treated patients column.

Summaries of TEAEs by maximum severity (mild, moderate, or severe) will be performed by SOC and PT. Patients with missing severities will be counted as severe. Summaries of TEAEs by maximum relationship will be performed by SOC and PT. Patients with missing relationship will be counted as probably related.

The denominator for percentages will be the number of patient within the cumulative dose group for the Safety Analysis Set. The total number of events will be presented

Client: Trevena, Inc.
Version #: 1.0
Version Date: 20Dec2016

Protocol/CIP #: CP130-3003

along with the patient count and percentage. For summaries by SOC and PT, SOCs will be sorted alphabetically. For summaries only by PT, the sort will be by descending frequency in the all treated patients column. PTs with the same frequency count will be sorted alphabetically.

AE data including start/end time, intensity, any action taken, outcome and whether or not it's serious will be listed for each patient by cumulative dose groups.

Lastly, scatterplots will be generated depicting patients' cumulative dose by duration of treatment for patients with at least 1 TEAE, patients with at least 1 related TEAE, patients with at least 1 TEAE leading to early discontinuation and patients with at least 1 SAE.

No statistical inference testing between the treatments will be performed for AEs.

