3.1.6 Follow up phase

A follow up contact will be made between 2 and 3 days after completion of the treatment phase. The contact may be conducted in person or by telephone. Concomitant medications and AEs/SAEs will be recorded.

The surgical procedure, medical diagnosis or ED diagnosis for which parenteral opioid therapy was warranted will be captured using the International Classification of Diseases, 10th Revision (ICD-10) terminology.

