3.6.2.1 Adverse Events

AEs occurring from time of informed consent to the follow-up phase will be recorded in source and will also be recorded in eCRF if the patient receives oliceridine. SAEs occurring from time of informed consent to the follow-up phase or 7 days after the last dose of oliceridine (whichever occurs later) will be recorded in source and eCRF; ongoing SAEs after this time frame will be followed until the investigator, medical monitor, and sponsor agree that the SAE is satisfactorily resolved. SAEs considered by the investigator to be related to oliceridine, regardless of the time of onset after treatment, should be reported.

AE reporting information is provided in [Section 4](#).

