6.3 Safety and Tolerability Analyses

The number and incidence of AEs/SAEs will be summarized overall and by severity and causality. MedDRA Version 19.0 will be used to classify all events with respect to system organ class and preferred term. WHODD (March 2016) will be used to categorize prior and concomitant medications. Summaries will include only treatment-emergent AEs (TEAEs) and will be summarized for the safety and tolerability analysis data set. Clinically significant changes in vital sign measurements, oxygen saturation measurements, somnolence/sedation scores, physical examination findings, and clinical laboratory assessments will be summarized via descriptive summary statistics.

Summary statistics for observed values and change from baseline values for vital sign measurements, oxygen saturation measurements, somnolence/sedation scores, physical examination findings, and clinical laboratory assessments will be summarized. Baseline values are defined as the last measurements taken before the first dose of oliceridine. SOWS total scores will be summarized.

Prior and concomitant medications will be summarized.

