6.3.2 Adverse Events

Adverse events includes any newly occurring event or previous condition that increased in severity or frequency from time of informed consent. AEs occurring from time of informed consent to the follow-up phase will be recorded in source documentation and will also be recorded in the EDC system if the patient receives oliceridine. All AEs must be recorded irrespective of whether or not they are considered medication-related. All AEs that are possibly or probably related to study medication will be followed until resolution or database lock, whichever occurs first. Changes in intensity or frequency of AEs should be recorded as separate events (i.e., a new record started).

Treatment emergent adverse events (TEAEs) are defined as AEs with onset at the time of or following the start of treatment with study medication until 7 days after the last dose of study medication or any pre-existing AEs that have worsened in severity on or after the first dose of study medication and through 7 days after the last dose of study medication.

Adverse events will be designated as treatment-emergent according to the following algorithm:

- If both the start date and start time of an AE are known, then:
- If the AE starts at any time prior to the time of the first dose on Day 1, then the AE will not be designated as treatment-emergent and hence will not be summarized.
- If the AE starts on or after the time of the first dose on Day 1 through 7 days after the last dose, then the AE will be designated as treatment-emergent.
- If only the start date of an AE is known and the start time of the AE is unknown, then:
- If the AE starts on Day 0, then the AE will not be designated as treatment-emergent and hence will not be summarized.

Client: Trevena, Inc.
 Version #: 1.0
 Version Date: 20Dec2016

Protocol/CIP #: CP130-3003

- If the AE starts on Days 1 through 7 days after the last dose, then the AE will be designated as treatment-emergent.

All AEs will be assessed on two descriptive parameters: intensity and relationship to the study medication:

- Intensity refers to the severity of an event and its impact on a patient's functioning. The following categories will be used to classify intensity:

Mild	Awareness of sign or symptom, but easily tolerated
Moderate	Discomfort enough to cause interference with usual activity
Severe	Incapacitating with inability to work or perform usual activity

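### A related SAE, including a related fatal event, that starts more than 7 days after the last dose is reportable but enters no planned adverse event table count

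*SAP*

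**What the plan says.** **Reporting.** Protocol 3.6.2.1 has two rules for SAEs. The general rule requires recording in source and eCRF from consent until the later of the follow-up phase and 7 days after the last dose. The second rule has no time limit: "SAEs considered by the investigator to be related to oliceridine, regardless of the time of onset after treatment, should be reported". Protocol 3.1.1, 4.2.2 and 4.2.3 repeat it, as does footnote 22 of the schedule in both documents, so the SAP itself carries the rule.

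**Last contact.** Protocol 3.1.6: "A follow up contact will be made between 2 and 3 days after completion of the treatment phase".

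**TEAE window.** SAP 6.3.2 defines TEAEs as "AEs with onset at the time of or following the start of treatment with study medication until 7 days after the last dose", together with pre-existing events that worsen in the same period. It makes no exception for related SAEs.

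**Tabulation.** SAP 8.6.3: "Summaries will include only TEAEs". Protocol 6.3 sets the same rule: "Summaries will include only treatment-emergent AEs (TEAEs) and will be summarized for the safety and tolerability analysis data set". The serious, fatal and discontinuation categories of the overall summary are each defined on TEAEs. The mock displays follow suit: Tables 14.3.2.1 to 14.3.2.8.1 are all TEAE tables. No table counts all SAEs, all deaths, or events after the window.

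**The concern.** The protocol deliberately keeps reporting open for the events that matter most to a safety study: serious ones that the investigator attributes to the drug. The analysis rule then closes the count at day 7 without saying what happens to such an event afterwards.

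The study has one arm, no hypothesis test and about 1000 patients, so the tabulated counts are the main result for the primary objective. A reader who sees a zero in a related or fatal row would take it to mean that no such event was reported. Under the plan as written it means that none was reported with onset by day 7.

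The case is not purely theoretical. Protocol 4.1.2 gives drug dependency or abuse as an example of an important medical event. Protocol 4.3.1 follows a pregnancy to its end and treats spontaneous abortion or congenital anomaly as an SAE. After a short course of treatment, such events could well start after day 7. Whether any would be judged related is for the investigator.

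**Working it through.** There is no stated figure to reproduce: SAP 4.4 gives about 1000 patients and no formal calculation. The check is to apply the rules in sequence to a related SAE.

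**Step 1: reporting against tabulation.** The follow-up contact falls 2 to 3 days after the treatment phase ends, so the 7-day limit is normally the later of the two recording limits.

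| Onset relative to last dose | Reportable if judged related | eCRF entry stated | TEAE (SAP 6.3.2) | Counted in AE tables (SAP 8.6.3) |
|---|---|---|---|---|
| From first dose to 7 days after last dose | Yes | Yes | Yes | Yes |
| More than 7 days after last dose | Yes | Not stated | No | No |

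The second line is the gap. It covers the serious, fatal, relationship, severity and SOC/PT tables alike, because all are built on TEAEs.

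**Step 2: the fatal row.** TEAE status depends on onset, not on date of death. An event that starts on day 5 and is fatal on day 12 is a TEAE with a fatal outcome and is counted. The exception comes from the recording rule in Protocol 4.2.1 and SAP 6.3.2, under which a change in intensity starts a new record. If the worsening on, say, day 9 is entered as a new record and the fatal outcome is attached to it, that record has its onset outside the window and the fatal row misses it.

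**Step 3: where the event could still be seen.** Three displays are not worded as TEAE-only:
- Listing 16.2.5.1 (adverse events, Enrolled Analysis Set), which shows seriousness, relationship and outcome.
- Figure 2.1.4, the scatterplot of patients with at least one SAE. It plots one dot per patient, with no event term, relatedness or outcome.
- The profiles in Listing 16.2.12.x, for patients treated longer than 96 hours only.

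None gives a count or a rate, and each needs the event to be in the clinical database.

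**Step 4: size, as illustration only.** Inputs: N = 1000 (SAP 4.4, approximate) and an assumed number x of omitted events. Exact (Clopper-Pearson) two-sided 95% limits:
- lower limit = 0.025 quantile of Beta(x, N − x + 1), or 0 when x = 0;
- upper limit = 0.975 quantile of Beta(x + 1, N − x). For x = 0 this is 1 − 0.025^(1/1000) = 0.37%.

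| x (assumed) | Rate | 95% limits |
|---|---|---|
| 0 (as the table would show) | 0% | 0 to 0.37% |
| 1 | 0.10% | 0.003% to 0.56% |
| 2 | 0.20% | 0.02% to 0.72% |
| 3 | 0.30% | 0.06% to 0.87% |

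The SAP plans no confidence intervals, and these limits assume complete ascertainment, which does not hold after day 7. They show only the order of magnitude.

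**The case against.** The strongest reply is that the 7-day cut is sensible. It coincides with the normal end of required SAE recording, and the last scheduled contact is earlier still. A related SAE starting after day 7 would surface only through unsolicited reporting. Putting such events into the ordinary serious and fatal rows would mix two kinds of ascertainment over one denominator, and would make inclusion depend on the investigator's causality judgement after day 7 but not before. This stands. It argues against widening the TEAE definition, but not against a separate, labelled row.

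A second reply is that the protocol and SAP agree. This also stands. A reader might infer that the SAP contradicts the protocol, but Protocol 6.3 sets the same TEAE-only rule. The gap lies between what is reported and what is tabulated. Nor are these events lost to safety oversight: Protocol 4.2.2 and 4.2.3 send SAE reports to the sponsor within 24 hours and on to the authorities as required.

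A third reply is that the impact is speculative. The documents give no expected number, and no threshold is set that one event would cross, so a claim that a single case would change the study's conclusion has no support. What remains is narrower: a table could show no related serious or fatal event when one had been reported.

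**Conclusion.** The point holds in a limited form and is a cheap improvement. Following the plan as written, a related SAE or related fatal event with onset more than 7 days after the last dose enters no AE table count. The expected number is not stated and is probably small after short intravenous treatment; one event in about 1000 patients is 0.1%.

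Three stronger readings are tempting and not supported:
- *The event would be invisible.* It could appear in Listing 16.2.5.1, in Figure 2.1.4 and, for the longest-treated patients, in a profile listing.
- *Any late death is left out.* A fatal event that starts by day 7 is counted whenever death occurs, unless late worsening is entered as a new record. An unrelated SAE that starts after the recording window need not be collected at all, so its absence is not due to the TEAE rule.
- *The data are already in hand.* The documents say that late related SAEs should be reported, but state eCRF entry only up to the later of follow-up and 7 days. Whether a late event reaches the database behind the listings is not established.

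The conclusion rests on reading the TEAE-only rule literally, which the mock displays support.

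**What to change.** Keep the TEAE definition and all TEAE rows unchanged. Then:

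1. In SAP 8.6.3 and mock Table 14.3.2.1, add two rows: *Related SAE with onset >7 days after last dose* and *Related fatal event with onset >7 days after last dose*, where related means possibly or probably related, as in SAP 6.3.2. Footnote both as not systematically ascertained, because no contact is scheduled that late.
2. State that late related SAEs are entered in the eCRF, or that the clinical database is reconciled with the safety database before lock. Without this the new rows could be empty for the wrong reason.

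The cost is a sentence or two in the SAP, one or two table rows and a reconciliation step. There are no added visits or patient burden. The reported SAE picture may become slightly less favourable.

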Oliceridine was evaluated for the treatment of moderate to severe acute pain following abdominoplasty in a double-blind, randomized, placebo- and active-controlled, phase 2 study. Study treatments were delivered by a patient-controlled analgesia (PCA) regimen, consisting of a loading dose, demand dose, and a lockout-interval. For the first half of the study, the oliceridine regimen was a 1.5 mg loading dose (as two 0.75 mg doses separated by 10 minutes), 0.1 mg demand doses, and a 6-minute lockout interval. The morphine regimen was a 4 mg loading dose (as two 2 mg doses separated by 10 minutes), 1 mg demand doses and a 6-minute lockout interval. As oliceridine was not previously administered in a PCA regimen, a prespecified interim analysis was planned to adjust the oliceridine PCA regimen after review of existing efficacy, safety and tolerability, and utilization data. For the second half of the study, the oliceridine demand dose was 0.35 mg with a 6-minute lockout interval. Oliceridine demonstrated statistically significant pain reduction compared to placebo and similar efficacy to morphine (oliceridine 0.1 mg regimen reduced average pain scores [LS mean change in time-weighted average over 24 hours] by 2.3 points [$P<0.0001$ vs. placebo]; oliceridine 0.35 mg by 2.1 points [$P=0.0003$ vs. placebo]; morphine, by 2.1 points [$P=0.0001$ vs. placebo]). The mean oliceridine utilization over the 24-hour treatment period for the 0.1 mg group was 7.6 mg, and for the 0.35 mg group, 14.8 mg. Rescue pain medication use was similar for both oliceridine (31% with oliceridine 0.1 mg, 21% with oliceridine 0.35 mg) and morphine (25%), and less than half the rate for placebo (64%; post hoc $P<0.0005$ for all three active groups vs. placebo). For the purpose of this study, hypoventilation events were defined as apparent and persistently decreased respiratory rate, respiratory effort or oxygen saturation. Oliceridine had a significantly lower prevalence of hypoventilation events, nausea, and vomiting than the morphine group (post hoc $P<0.05$ for both oliceridine regimens vs. morphine):

Trevena, Inc.

Protocol CP130-3003

Version 5.0

14 Sep 2016

	Placebo	Oliceridine 0.1 mg	Oliceridine 0.35 mg	Morphine
Hypoventilation	10%	15%	31%	53%
Vomiting	8%	15%	15%	42%
Nausea	18%	41%	46%	72%

Oliceridine preclinical and clinical data are summarized in the current investigator's brochure (IB).

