4.3.2 Individual Patient Stopping Criteria

Oliceridine is a μ -opioid receptor agonist; therefore, effects on BP and respiration should be anticipated.

As with conventional opioids, oliceridine will be administered PRN; for a patient, analgesia must be balanced with intolerability. In a situation of significant intolerability, temporary or permanent discontinuation may be warranted:

- Asymptomatic decreased BP, increased HR, or decreased or increased RR may require only temporary discontinuation without additional intervention.
- Symptomatic hypotension, tachycardia, advancing somnolence/sedation, or respiratory signs (bradypnea, tachypnea, decreased respiratory effort, and/or decreased oxygen saturation) require temporary discontinuation and may require additional intervention.
- Symptomatic hypotension, tachycardia, advancing somnolence/sedation, or respiratory signs (bradypnea, tachypnea, decreased respiratory effort, and/or decreased oxygen saturation) requiring urgent intervention also requires permanent discontinuation.
- Possibly or probably related increase in QTcF to ≥ 500 milliseconds, or increase in QTcF of > 60 milliseconds versus most recent pre-exposure QTcF requires: permanent discontinuation; urgent clinical laboratory assessment and correction of electrolyte abnormalities (eg, hypocalcemia, hypokalemia, hypomagnesemia); and hourly ECG until QTcF < 500 milliseconds.

Additionally, if a patient receives 60 mg of oliceridine within the first 12 hours, the patient will early discontinue oliceridine and will be managed conventionally. The assigned reason for early discontinuation will be “other” and with the comment “dosing limit” (see [Section 3.5.2.3](#)).

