4.4 Determination of Sample Size

No formal sample size calculations were made. Approximately 1000 patients will be treated with oliceridine.

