Patients are counted once within each system organ class and each preferred term.

TEAEs are defined in section 6.3.3 of the SAP.

Trevena, Inc.
Protocol CP130-3003

CONFIDENTIAL
Page x of y

Use the same template as for Table 14.3.2.2.1 for the following tables:

Table 14.3.2.2.1.1

Treatment Emergent Adverse Events (TEAE) by System Organ Class and Preferred Term by CYP2D6 Metabolizer Status
(Safety Analysis Set)

Table 14.3.2.2.1.2

Treatment Emergent Adverse Events (TEAE) by System Organ Class and Preferred Term by BMI Category
(Safety Analysis Set)

Table 14.3.2.2.2

Serious Treatment Emergent Adverse Events (TEAE) by System Organ Class and Preferred Term
(Safety Analysis Set)

Table 14.3.2.2.2.1

Serious Treatment Emergent Adverse Events (TEAE) by System Organ Class and Preferred Term by CYP2D6 Metabolizer Status
(Safety Analysis Set)

Table 14.3.2.2.2.2

Serious Treatment Emergent Adverse Events (TEAE) by System Organ Class and Preferred Term by BMI Category
(Safety Analysis Set)

Table 14.3.2.2.3

Treatment Emergent Adverse Events (TEAE) Resulting in Early Discontinuation by System Organ Class and Preferred Term
(Safety Analysis Set)

Table 14.3.2.2.3.1

Treatment Emergent Adverse Events (TEAE) Resulting in Early Discontinuation by System Organ Class and Preferred Term by
CYP2D6 Metabolizer Status
(Safety Analysis Set)

Table 14.3.2.2.3.2

Treatment Emergent Adverse Events (TEAE) Resulting in Early Discontinuation by System Organ Class and Preferred Term by
BMI Category
(Safety Analysis Set)

Table 14.3.2.3.1
Treatment Emergent Adverse Events (TEAE) in Decreasing Frequency of Preferred Term
(Safety Analysis Set)

Preferred Term	Oliceridine <= 4 mg N=XXX n (%) [E]	Oliceridine >4 to 8 mg N=XXX n (%) [E]	Oliceridine >8 to 16 mg N=XXX n (%) [E]	Oliceridine >16 to 36 mg N=XXX n (%) [E]	Oliceridine >36 mg N=XXX n (%) [E]	All Treated Patients N=XXX n (%) [E]
Patients with at Least 1 TEAE	xxx (xxx.x) [xxx]	xxx (xxx.x) [xxx]	xxx (xxx.x) [xxx]	xxx (xxx.x) [xxx]	xxx (xxx.x) [xxx]	xxx (xxx.x) [xxx]
<Preferred term 1>	xxx (xxx.x) [xxx]	xxx (xxx.x) [xxx]	xxx (xxx.x) [xxx]	xxx (xxx.x) [xxx]	xxx (xxx.x) [xxx]	xxx (xxx.x) [xxx]
<Preferred term 2>	xxx (xxx.x) [xxx]	xxx (xxx.x) [xxx]	xxx (xxx.x) [xxx]	xxx (xxx.x) [xxx]	xxx (xxx.x) [xxx]	xxx (xxx.x) [xxx]
...						
<Preferred term n>	xxx (xxx.x) [xxx]	xxx (xxx.x) [xxx]	xxx (xxx.x) [xxx]	xxx (xxx.x) [xxx]	xxx (xxx.x) [xxx]	xxx (xxx.x) [xxx]

Note: E = Number of events.

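### The SAP prespecifies no patient-level count of respiratory-depression events, so their incidence cannot be read from any planned table

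*SAP*

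**What the plan says.** Safety and tolerability is the primary objective (Protocol 2.1, SAP 3). Both introductions name respiratory depression among the adverse events that limit opioid use. Protocol 1.1 reports the phase 2 abdominoplasty study with a composite, in which "hypoventilation events were defined as apparent and persistently decreased respiratory rate, respiratory effort or oxygen saturation". The rates given are 10% on placebo, 15% and 31% on the two oliceridine regimens, and 53% on morphine. Protocol 4.3.2 also names "respiratory signs (bradypnea, tachypnea, decreased respiratory effort, and/or decreased oxygen saturation" together in its individual stopping criteria.

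SAP 8.6.3 carries no such grouping forward. It plans an overall summary and then two uncut tabulations: "The number and percentage of patients with TEAEs for each cumulative dose group and overall will also be displayed by SOC and PT", and "TEAEs will also be summarized by PT only". A further table shows the most common events, "where PTs occurring in at least 5% of the all treated patients group will be included". The footnote to mock Table 14.3.2.2.1 gives the counting rule: "Patients are counted once within each system organ class and each preferred term". Serious events, events leading to discontinuation, maximum severity, maximum relationship, and dose-by-time displays use the same SOC and PT levels or the any-TEAE level.

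Outside the adverse event tables, SAP 6.3.8 and mock Table 14.3.5.1.1 count patients with SpO2 below 90%. SAP 6.3.4 sets abnormality criteria for blood pressure and pulse but none for respiratory rate.

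**The concern.** Anyone reading the study report of an opioid will ask how many treated patients had a respiratory-depression event. A single patient may have several related terms recorded, and different patients may have the same clinical picture recorded under different terms. Counting patients within each PT does not answer the question, because the PT rows do not show how far they overlap.

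Without a grouping fixed in advance, someone will have to choose the terms later. The study is open-label, SAP 7.4 plans no data monitoring committee, and the same section expects an interim analysis to support regulatory discussions. Terms chosen after the data have been seen leave the figure open to dispute.

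The SAP does specify unions elsewhere: AST or ALT at or above 3 and 5 times the upper limit (SAP 6.3.3), and possibly and probably related events combined (SAP 6.3.2).

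**Working it through.** **Inputs**
- Planned number treated: "Approximately 1000 patients will be treated with oliceridine" (SAP 4.4).
- Display cut for the most-common table: 5% of all treated patients, applied to each PT (SAP 8.6.3).
- Phase 2 hypoventilation on oliceridine: 15% and 31% (Protocol 1.1, no group sizes given).
- The number of related PTs and their overlap are not in the documents. They are assumptions, shown as ranges.

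The plan states no derived figure on this point, so there is nothing to reproduce.

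**Step 1: the cut.** 0.05 × 1000 = 50 patients. A PT recorded in 49 patients (4.9%) is left out of mock Table 14.3.2.6.1.

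**Step 2: what PT rows say about the total.** For PT counts n₁ to n_k, the number of patients with any of the terms lies between max(nᵢ) and the sum of the nᵢ. If the terms occur independently at a common rate q, it is N × [1 − (1 − q)^k]. With every PT at 49 of 1000:

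| Number of PTs | Full overlap | Independent | No overlap |
|---|---|---|---|
| 2 | 49 | 95.6 | 98 |
| 3 | 49 | 139.9 | 147 |
| 4 | 49 | 182.1 | 196 |

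For three PTs the independent case is 1000 × (1 − 0.951³) = 139.9. The same three rows are therefore compatible with 4.9%, 14.0% or 14.7% of patients.

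**Step 3: sensitivity to sample size.** The three-PT upper bound hardly moves: at 900 patients the cut is 45 and 3 × 44 / 900 = 14.7%; at 1100 the cut is 55 and 3 × 54 / 1100 = 14.7%.

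**Step 4: whether another planned output supplies the count.**
- SOC rows count each patient once but include unrelated events, and the documents do not say whether all the component terms share one SOC.
- SpO2 <90% is a per-patient count, but of one component only.
- Respiratory rate is summarised by means and changes. SAP 6.2.4 selects the one value nearest the window midpoint, so a low reading can drop out of the summary.
- Respiratory effort has no planned measurement; adverse event terms are its only source.
- Event totals are no substitute for patient counts, because Protocol 4.2.1 starts a new record when intensity or frequency changes.

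None of these gives the number of patients with any respiratory-depression event.

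**The case against.** The strongest reply is that the information is not lost. Listing 16.2.5.1 shows SOC, PT and verbatim term for each patient, so a once-per-patient count can be made. That stands: what is missing is a prespecified definition and a table row, not the data.

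A reader might infer that a respiratory problem could vanish because of the 5% rule. The documents do not support this. The rule applies to single PTs in one table. Mock Tables 14.3.2.2.1 and 14.3.2.3.1 have no cut, so every respiratory PT is still reported.

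A reader might also infer that events at the phase 2 rates would be wholly absent from the most-common table. That needs a particular pattern of coding. With three PTs, a 15% composite is 150 patients, so the PT counts average at least 50 and at least one PT meets the cut. Under an even split without overlap, 15% needs four PTs (150 / 4 = 37.5), and 31% needs seven (310 / 7 = 44.3, against 310 / 6 = 51.7). The documents give no number of terms, and Protocol 4.2.1 asks for a diagnostic term whenever possible, which limits splitting. With no overlap, moreover, the PT rows add up exactly to the total.

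Two further limits stand. The list in Protocol 4.3.2 includes tachypnea and sits beside hypotension and sedation, so it is not a definition of hypoventilation. A PT list would also not reproduce the phase 2 measure. That definition required apparent and persistent decreases. Protocol 4.1.1 leaves out signs anticipated in surgical or medical patients unless they are worse than expected, and the population and regimens differ.

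**Conclusion.** The concern holds in a limited form. No planned table gives the number of patients with any respiratory-depression or hypoventilation event, and the planned rows only bound it: in the three-PT example, 49 to 147 of 1000 patients. That range rests on an assumed number of terms, equal counts just under the cut, and unknown overlap. It illustrates the ambiguity and does not predict the result.

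A count remains possible afterwards, but with terms selected once open-label results are known. Component PTs below 5% would be missing from the most-common table while remaining in the uncut ones; with three such PTs, up to 14.7% of patients could be affected without any of the terms appearing there. This does not invalidate the safety analysis. It is a cheap improvement worth making, because it bears on the primary objective and uses only data already collected.

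**What to change.** Before the interim analysis, have medical review fix a PT list covering decreased respiratory rate, decreased respiratory effort, decreased oxygen saturation or hypoxia, and respiratory depression. State explicitly whether tachypnea is excluded.

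Add to SAP 8.6.3 and mock Table 14.3.2.1 a row for patients with at least one respiratory-depression TEAE, counted once per patient, by cumulative dose group and overall, shown whatever its frequency. Because the subgroup tables reuse that template, the row would carry through to them. An exact 95% confidence interval is optional and is compatible with a plan that makes no tests. Sub-rows for naloxone or oxygen given for the event are also optional; they would need the medication-to-event link shown in Listing 16.2.2.2.

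State that any comparison with the phase 2 rates is descriptive only, because definition, population and regimen differ.

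The cost is one term list, a sentence or two of SAP text, one table row and a little programming. The headline respiratory figure may look less favourable than separate PT rows would.
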